On Day 1 of the study (initiation of study drug injections), all subjects will receive a SC injection of 300 mg of buprenorphine in RBP-6000. Subsequent doses of RBP-6000 may be adjusted down to 100 mg and back up to 300 mg based on the medical judgment of the Investigator. After injection of RBP-6000, subjects will not be permitted to receive supplemental SUBOXONE sublingual film during the RBP-6000 treatment period. Subjects who require supplemental SUBOXONE sublingual film or other sublingual buprenorphine pharmacotherapy during the RBP-6000 treatment period will be withdrawn from the study and referred for appropriate treatment.

Subjects will return to the clinic for monthly injection visits (every 28 - 2/+ 4 days) for a total of up to 12 injections for *de novo* subjects or for a total of 6 injections for roll-over subjects. ECG recordings and vital signs will be collected pre and post each SC injection. All ECGs will be interpreted by a central monitoring facility. Subject-reported injection site pain Visual Analog

Scale scores (VAS) will be collected at various times up to 1 hour after each injection. Local injection site grading will be collected at various time points starting immediately after injection and will be evaluated for pain, tenderness, warmth, itching, erythema, inflammation or swelling, and bruising using a 4-point severity scale. At each visit after injections begin, the injection site will be assessed by site staff and will also be evaluated for evidence of attempts to remove the depot.

Subjects will need to return to the clinic weekly for the first 5 weeks and biweekly (i.e., every 2 weeks) until injection 6, and monthly for the rest of the study period for urine drug screens (UDS), Timeline Followback (TLFB) interviews, opioid craving VAS evaluation, COWS and subject reported outcomes (Subjective Opiate Withdrawal Scale [SOWS]). Subjects will continue to receive counseling (manual-guided behavioral therapy) during the study.

Safety assessments will be collected at each visit and will include the following: vital signs, electronic Columbia Suicide Severity Rating Scale (eC-SSRS) responses, ECGs, laboratory tests (hematology, chemistry, urinalysis, and pregnancy test), concomitant medications, and AEs.

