### 6.15.5 Ancillary Medications

Treatment of signs and symptoms of opioid withdrawal after enrollment can be treated with ancillary medications allowed by the protocol, as clinically indicated by the Investigator or

physician Sub-Investigator. Subjects whose symptoms are not manageable will be discontinued from the study and will be followed up according to the procedures described in the SOE (EOS/ET Visit; [Appendix 3](#) and [Appendix 5](#)) and Section 6.14.

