### 9.2 Determination of Sample Size

There is no formal sample size calculation. Approximately 300 *de novo* subjects as well as approximately 300 subjects who completed the RB-US-13-0001 efficacy study will be enrolled into this study to ensure at least 100 subjects reach 1 year of treatment with RBP-6000.

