## 9.8 Handling of Missing Data

For dichotomous outcome measures such as UDS results (negative; non-negative) and self-reports for illicit opioid use (negative; non-negative), any missing observation will be recorded as “non-negative.” For all continuous endpoints (e.g., COWS, SOWS, and VAS), the missing data mechanism will be assumed to be either missing completely at random (MCAR) or missing at random (MAR). The missing data will not be imputed because the analysis method, mixed model for repeated measures (MMRM), does not require any imputation and no sensitivity analyses will be performed on these variables. For time-to-event variables, if the event of interest is not observed prior to withdrawal or end of treatment, the observations will be censored at the time of withdrawal or at the end of treatment. For example, if some subjects still have not had a urine sample negative for opioids combined with self-reports negative for illicit opioid use when the study ends or at the time of withdrawal from the study, then the time to first urine sample negative for opioids combined with self-reports negative for illicit opioid use will be censored at the last time they were assessed.

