1.1 Changes from Protocol

The following changes to the analysis planned in the protocol were made:

- The addition of an analysis set (Run-In Safety Analysis Set) was made to aid in the analysis of the Run-In period.
- Electrocardiograms (ECGs) overall impression summaries will only be summarized by normal or abnormal; protocol says they should be summarized by normal, abnormal not clinically significant, or abnormal clinically significant, but there is no distinction of clinical significance for abnormal results.
- There will be no mixed-effect model for repeated measure analysis on the clinical outcome data, Clinical Opiate Withdrawal Scale (COWS), Subjective Opiate Withdrawal Scale (SOWS), and Opioid Craving Visual Analog Scale (VAS), due to the nature of the study design.
- The Clinical Outcome Assessment Analysis Set has been removed since this is a safety study.
- Total score for electronic Columbia Suicide Severity Rating Scale will not be summarized.
- Physical examination data is collected as a part of the corresponding safety assessment (i.e. adverse events (AEs), vital signs).

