9.0 Statistical Methods

All statistical analyses will be performed using SAS® Version 9.4 or higher.

Categorical variables will be summarized using counts and percentages. Percentages will be rounded to one decimal place; except 100% will be displayed without any decimal places and percentages will not be displayed for zero counts. When assessments are not applicable (ie Post injection 6 visits for roll-over subjects), an N/A will displayed instead of a zero,

Sponsor: Indivior Inc.
Protocol no: RB-US-13-0003

Continuous variables will be summarized using the number of observations (n), mean, standard deviation (SD), median, minimum, and maximum. The minimum, maximum, and 95% CI values (in some instances) will be displayed to the same level of precision as the raw data, the median and mean to one additional decimal place and the SD to two additional decimal places. The maximum number of decimal places will be 4. All summaries will be presented by subject type (de novo or roll-over) unless otherwise stated.

Unless otherwise stated, summaries will be presented by subject type (de novo or roll-over and total). Missing values will be presented by blank spaces. For partially missing dates, the information present will be printed; e.g., "--JAN2000".

For dichotomous outcome measures such as urine drug screen results (negative; non-negative) and self-reports for illicit opioid use (negative; non-negative), any missing observation will be set equal to "non-negative." Missing results for substances other than opioids will not be imputed. For all continuous endpoints (e.g., COWS, SOWS, and VAS), the missing data will not be imputed.

Only scheduled assessments per protocol Amendment 4 will be presented in tables and figures except for worst case post-baseline and at any time types of analyses (all post-baseline including unscheduled assessments data will be considered for this derivation) but all data will be presented in the listings.

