9.5.2 Clinical Opioid Withdrawal Scale (COWS) Total Score

COWS total scores will be summarized by clinical visit and subject type using descriptive statistics (mean, median, SD, minimum, and maximum), including change from baseline. A listing of the COWS assessment will be provided for the Safety Analysis Set. Additionally, separate listings for the actual values (individual responses and total scores) and the change from baseline in total COWS score will be presented for the Safety Analysis Set.

A figure for the COWS scores over time will be created for all subjects in the Safety Analysis Set. An additional table and figure will be created for the Safety Analysis Set excluding subjects using illicit opioids (either by UDS or TLFB) at any time during the study.

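### With the MMRM dropped and nothing put in its place, by-visit COWS, SOWS and craving means describe only subjects still attending and can fall through dropout alone

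*SAP*

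**What the plan says.** Protocol 9.8 assumes that missing continuous scores are missing completely at random or missing at random. It gives one reason for leaving them alone: "The missing data will not be imputed because the analysis method, mixed model for repeated measures (MMRM), does not require any imputation". It also rules out sensitivity analyses for these variables.

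SAP 1.1 lists a change: "There will be no mixed-effect model for repeated measure analysis on the clinical outcome data". The reason given is the study design. SAP 9.0 keeps the other half of the rule: "For all continuous endpoints (e.g., COWS, SOWS, and VAS), the missing data will not be imputed".

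What remains is descriptive. SAP 9.5.2 states that "COWS total scores will be summarized by clinical visit and subject type using descriptive statistics", with change from baseline and a figure over time; 9.5.3 and 9.5.4 do the same for SOWS and Opioid Craving VAS. The one supplementary table and figure per scale leaves out anyone who used illicit opioids during the study. Under SAP 5.0 an early-termination (ET) score is mapped to the visit window in which it falls, and the subject contributes nothing after that.

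Two protocol rules link leaving to the outcome. Section 6.15.5: "Subjects whose symptoms are not manageable will be discontinued from the study", where the symptoms are those of opioid withdrawal. Section 3.1, repeated in 5.2.3: "Subjects who require supplemental SUBOXONE sublingual film or other sublingual buprenorphine pharmacotherapy during the RBP-6000 treatment period will be withdrawn from the study".

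**The concern.** A mean over whoever attends a visit describes the treated population only if leaving is unrelated to the score. A likelihood-based repeated-measures model needs less: leaving may depend on scores already observed. Removing the model while keeping non-imputation therefore moves the plan, without saying so, from a missing-at-random assumption to missing completely at random. The two discontinuation rules make the latter implausible.

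The direction favours the drug. Entry already requires COWS of 12 or less and craving of 20 mm or less (Protocol 4.4), so the informative course afterwards is deterioration, and subjects who deteriorate tend to leave the later means. Clinical outcome is the secondary objective, and SAP 9.5 reports these scales under efficacy. A low or falling curve to Week 49 would be read as lasting control of withdrawal and craving, when part or all of the fall could be a change in who is being averaged.

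**Working it through.** **1. Who is affected.** De novo subjects are scored to Day 337, roll-over subjects to Day 169 (schedules of events, Protocol Appendices 3 and 5). Drift over the year is therefore a de novo matter, and after Week 25 the total column contains de novo subjects only.

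**2. Inputs.** The plan states no SD, dropout rate or expected course for these scales, so it has no figure to reproduce. The only number bearing on retention is the enrolment of about 300 + 300 "to ensure at least 100 subjects reach 1 year of treatment with RBP-6000": 100/300 = 33.3% if all were de novo, or 100/600 = 16.7% of everyone. That is an exposure floor, not a forecast. Retention of 33% and 50% is taken as an assumed range.

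**3. Simulation A (no true change).** 60,000 subjects per scenario, 20 visits from Day 1 to Day 337. Standardised score Y = b + e, with var(b) = r, var(e) = 1 - r, and r = 0.3, 0.5 or 0.7. The hazard of leaving between visits is proportional to (gap length) x h^(last score), with h = 1.5 or 2 per SD, scaled to give the chosen retention. Bias in the observed Day 337 mean, in SD:

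| Retention | h | r = 0.3 | r = 0.5 | r = 0.7 |
|---|---|---|---|---|
| 33% | 1.5 | -0.13 | -0.21 | -0.29 |
| 33% | 2 | -0.20 | -0.34 | -0.46 |
| 50% | 1.5 | -0.08 | -0.14 | -0.19 |
| 50% | 2 | -0.13 | -0.21 | -0.30 |

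If COWS had an SD of 3 (assumed), 33% retention gives 0.13 x 3 = 0.4 to 0.46 x 3 = 1.4 points, and 50% gives 0.08 x 3 = 0.2 to 0.30 x 3 = 0.9 points.

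In the same 12 scenarios the observed change from baseline is off by only 0.00 to +0.02 SD. With flat individual courses, those who stay also had lower baselines, and the selection cancels.

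**4. Simulation B (different dropout model, ET score kept in its own window as in SAP 5.0).** Score with mean 4 and SD 3, 12 post-baseline visits, log-odds of leaving +1 per SD of current score. True mean change is +0.02 to +0.03 points with flat courses and +0.09 with individual slopes (slope SD 2 to 3 points per year, r = 0.5). Results at the last visit, in points:

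| Dropout | Flat: mean vs baseline mean | Slopes vary: mean vs baseline mean | Slopes vary: observed change from baseline |
|---|---|---|---|
| 30% | -0.21 to -0.62 | -0.56 to -0.79 | -0.17 to -0.40 |
| 50% | -0.46 to -1.09 | -1.01 to -1.42 | -0.28 to -0.73 |
| 67% | -0.67 to -1.58 | -1.56 to -2.07 | -0.45 to -0.98 |

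With flat courses the observed change showed no false improvement (+0.02 to +0.25). As a control, 50% dropout unrelated to score moved the mean by +0.05. Counting the ET score once does not remove the drift.

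**5. Mixed model on the same data.** In A it lay between -0.02 and +0.04 SD of the truth at 33% retention and between -0.07 and +0.02 SD at 50%. In B it estimated +0.03 to +0.14 points with flat courses and +0.08 to +0.14 with varying slopes. Both simulations satisfy missing at random and the fitted model matched how the data were generated, so this is a favourable test.

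**The case against.** The best defence is that nothing was hidden or specially chosen. SAP 1.1 declares the removal, and Protocol 9.1 says deviations from its analyses will be included in the SAP. Protocol 9.6.1 itself plans only descriptive statistics for these scales; the MMRM appears in 9.8 and the abbreviation list, with no covariates or covariance structure. A reader might infer that a specified efficacy analysis was abandoned. The documents do not support that: what was lost is the reason for not imputing.

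A reader might also infer that these scales are treated worse than everything else. They are not. Vital signs and injection-site pain (SAP 9.6.3, 9.6.4.4) are by visit or time point only, and continuous laboratory values and ECG intervals are also summarised as observed. What laboratory data and ECGs have in addition is a shift table to the last on-treatment result, or to end of study/early termination (9.6.2, 9.6.4.1). Missing opioid results are set to non-negative.

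Attrition is visible: SAP 9.0 gives n, 9.1 gives disposition with reasons, 9.6.1.3 covers adverse events leading to discontinuation and 9.6.1.5 withdrawal-type events. This stands, but it shows the loss without correcting the means.

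The size is also open to challenge. Early stopping once the exposure target is met (Protocol 3.3, SAP 3.3) would be unrelated to scores, whereas the simulations make all loss score-dependent. They also ignore the truncation of scores at entry. Both points are fair. Finally, for subjects withdrawn because they need other buprenorphine, a repeated-measures model estimates a hypothetical score under continued treatment. That is a reason to label it, and to put the last on-treatment row first.

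**Conclusion.** The point holds for the visit means and the over-time figures. The plan keeps a no-imputation rule whose only justification has gone, and the protocol makes leaving depend on the outcome. Under the assumed inputs (33-50% retention, hazard x1.5-2 per SD, within-subject correlation 0.3-0.7, no true change) the Week 49 observed mean is about 0.1-0.5 SD too low. With no SD or dropout rate in the documents, this shows what the plan permits; it does not predict this study's results.

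It would be tempting to conclude that any reported improvement is an artefact. The documents and the arithmetic do not support that. The change-from-baseline summaries are planned alongside the means; they are essentially unbiased when individual courses are flat and falsely negative only when courses vary between subjects. Nor is one-third retention a planning assumption. The study is single-arm with no planned test or comparison of subject types, so the consequence is a misleading descriptive display of a secondary outcome. It should be corrected, but the primary safety analysis is untouched.

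**What to change.** Keep the observed-case tables and make these additions for COWS, SOWS and Opioid Craving VAS:

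1. A row for the last on-treatment assessment (including ET), with change from baseline, for all Safety Analysis Set subjects, in line with the existing laboratory and ECG shift tables. Label it as status on leaving treatment, not as a Week 49 estimate.
2. The number of subjects at each visit on the figures, if the separate table and figure shells do not already show it.
3. As a supportive descriptive estimate, the repeated-measures model named in Protocol 9.8, fitted within subject type, with visit as a factor, baseline as a covariate and ET scores included. Report means and 95% CIs by visit, and state that it relies on missing at random and estimates scores as if treatment had continued.
4. In SAP 1.1, replace the study-design reason with text describing this approach; a single-arm design does not prevent such a model.

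Cost: SAP wording, one row and one model per scale, and a little programming. No new data are needed, because all three scales are already scheduled at the EOS/ET visit. Late-visit results may look less favourable.

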9.1 Subject Disposition

The number and percentage of all screened subjects in each analysis set will be summarized (de-novo, roll-over and total).

A summary of the number and percentage of all screen and enrolled subjects (de-novo, roll-over, total) at each center will be presented, including those centers who screened or enrolled no subjects.

The number and percentage of subjects screened, screen failures, entered the Run-In period, Run-In failures (including those who prematurely discontinued during the Run-In period), entered the RBP-6000 treatment period (i.e. received at least 1 dose of RBP-6000), and who completed the study will be presented, together with the number and percentage of subjects who prematurely discontinued from the RBP-6000 treatment period or in the Run-In period prematurely and a breakdown of the corresponding reasons for study discontinuation separately in each period.

A listing of all subjects' analysis set inclusions, disposition, and reasons for study discontinuation will be presented.

A listing of the inclusion/exclusion reasons for screen failure will be provided.

9.2 Protocol Deviations

A listing of subjects in the Safety Analysis Set with important protocol deviations (PDV) will be provided. An important deviation is defined as:

- Subject consent was never obtained
- Inclusion/Exclusion/Enrollment Criteria were violated

9.3 Demographic and Baseline Characteristics

Demographic and baseline characteristics (sex, ethnicity, race, age [years and categories of ≥ 18 -<30, ≥ 30 -<45, ≥ 45 -<60, ≥ 60 , and ≥ 65], weight [kg], height[cm], waist-to-hip ratio, body mass index [BMI; kg/m²], tobacco use [never, former, current], caffeine use [never, former, current], alcohol use [never, former, current]) will be summarized by subject type (de novo, roll-over and total) using descriptive statistics for subjects in the Safety Analysis Set. Qualitative variables (sex, ethnicity, race, age categories, tobacco use, caffeine use, alcohol use) will be summarized using frequencies while quantitative variables (age, weight, height, BMI, waist-to-hip ratio) will be summarized using mean, SD, median, minimum, and maximum. Demographic and baseline data will also be listed for all screened subjects.

Sponsor: Indivior Inc.
Protocol no: RB-US-13-0003

A further summary of the subjects will be presented for subgroups including opioid users at screening [injectable vs. non-injectable] and use of opioids during the Run-In period as indicated by a nonnegative UDS in the Safety Analysis Set.

History of drug use will be presented by substance and previous use for subjects in the Run-In Safety Analysis Set. All drug use history collected on the CRF will be listed including days of opioid drug use in the past 30 days, years of regular drug use in lifetime, and route the substance was administered for all screened subjects.

9.3.1 Medical History

Medical history will be coded using Medical Dictionary for Regulatory Activities (MedDRA) version 17.1 and summarized by the number and percentage of subjects in each system organ class (SOC), preferred term (PT), and subject type in the Safety Analysis Set.

Listings of medical history events for subjects in the Run-In Safety Analysis Set will be provided.

9.3.2 Prior and Concomitant Medications

Medications received prior to exposure to SUBOXONE, categorized by preferred name and ATC level 4 class according to World Health Organization Drug Dictionary (WHODRUG; Version 2014SEP01DDE), will be summarized for the Safety Analysis Set. The number and percentage of subjects using each medication will be displayed together with the number and percentage of subjects using at least one medication. Additionally, medications received concomitantly with study will be summarized in the same manner for the Safety Analysis Set.

All prior and concomitant medications will be presented in separate listings for the Safety Analysis Set.

9.4 Study Treatment Exposure

A summary of the exposure to SUBOXONE during the Run-In period will be summarized by Run-In period (induction/dose adjustment), visit, administration/dispensation, and dosage for the Run-In Safety Analysis Set. A listing of SUBOXONE exposure (administration/dispensation) will be provided.

Exposure will be derived as date of first RBP-6000 injection on the RB-US-13-0003 study, to 28 days after the last RBP-6000 injection on this study.

The duration of exposure in the 0-<4 weeks through 48 – <52 weeks, total number of RBP-6000 doses received, the total number of actual doses as a continuous summary, and the total number of actual doses as a categorical summary will be presented for the Safety Analysis Set. RBP-6000 exposure data will also be listed detailing the dose of RBP-6000 received at each injection and the number of days between injections.

The number of subjects who have early removal of the RBP-6000 depot by physician will be presented for the Safety Analysis Set. Early removal of the study drug depot data including the reason and removal date and time will be listed.

9.5 Efficacy Analysis

All efficacy endpoints will be summarized for the Safety Analysis Set.

Sponsor: Indivior Inc.
 Protocol no: RB-US-13-0003

9.5.1 Self-reported and Urine Samples Illicit Drug Use

Urine Drug Screen Result

A subject will be deemed to have a 'non-negative' result for opioids when his/her urine drug screen result is greater than the upper limit of normal for any of the opioid drugs tested ([Section 9.6.2.4](#)).

Opioid Drug Classification (UDS)

Drug	Opioid?
Amphetamine	No
Barbiturates	No
Benzodiazepine	No
Benzoyllecgonine	No
Buprenorphine ¹	No
Cannabinoids	No
Codeine	Yes
Hydrocodone	Yes
Hydromorphone	Yes
Methadone	Yes
Morphine	Yes
Opiate	Yes
Oxycodone	Yes
Oxymorphone	Yes
Phencyclidine	No

¹ Buprenorphine urine testing for de novo subjects was only included during the screening period; and urine testing for buprenorphine during the screening period was subsequently removed from the protocol per protocol amendment #1. The only subjects who tested positive during screening (when RBP-6000 was not being administered) were de novo subjects. Roll-over subjects were not tested for buprenorphine during screening. Neither de novo nor roll-over subjects were tested for buprenorphine at baseline or post-RBP-6000 administration.

Opioid Drug Classification (TLFB)

Drug	Opioid?
Amphetamine/Methadone ¹	Yes
Barbiturates	No
Benzodiazepine	No
Buprenorphine	Yes
Cocaine	No
Ethanol	No
Methadone	Yes
Opioids	Yes
PCP	No

¹ The TLFB interview called for an assessment of the use of amphetamine/methamphetamine. However, the ePRO tablet was programmed to ask for the use of amphetamine/methadone. As a result, the primary analysis for the TLFB question of amphetamine/methadone will be assumed to be non-negative. A sensitivity analysis will be performed where the answer to the TLFB question of amphetamine/methadone of 'Use' will be assumed to be negative.

Subjects' self-reported illicit drug use from the TLFB and opioid detection from the UDS will be summarized together by showing the number and percentage of subjects who have ≥ 0 , $\geq 10\%$, $\geq 20\%$, $\geq 30\%$, $\geq 40\%$, $\geq 50\%$, $\geq 60\%$, $\geq 70\%$, $\geq 80\%$, $\geq 90\%$, $\geq 100\%$ negative result and a continuous summary of the percent negative. The cumulative distribution function (CDF) of the percentage abstinence (negative self-reports from the TLFB combined with negative UDS for opioid use) will be presented in a graph. The graph will present the proportion of subjects who remained at least a given percentage abstinent from opioid drug

Sponsor: Indivior Inc.
Protocol no: RB-US-13-0003

use, as defined in [Section 5](#); for example, 10% on the x-axis represents the proportion of subjects who had at least 10% of their self-reported opioid drug use combined with UDS as abstinent.

Additionally, a table showing the percentage of subjects with negative results at each visit will be provided.

All missing results for opioids were considered nonnegative for opioids. Opioids non-negative indicates detection of buprenorphine (only self-reports), codeine, hydrocodone, hydromorphone, methadone, morphine, opiates, oxycodone, and oxymorphone in the urine drug screen and reporting of amphetamine/methadone, buprenorphine, methadone, and opioids use in the timeline followback.

The number and percentage of subjects abstinent between visits will be summarized by subject type for the Safety Analysis Set. Additionally, the time to first urine sample non-negative or TLFB self-report of non-negative for opioids will be analyzed in the Safety Analysis Set for subjects who are Abstinent on Day 1 using Kaplan-Meier analysis methods to determine the first quartile (25%) and median (days) along with their corresponding confidence intervals in each subject type and overall. Subjects who are abstinent throughout the trial will be censored on the date of their last negative urine sample of TLFB self-report for opioids.

The number and percentage of subjects who have a non-negative result in each substance tested in the UDS will be reported by subject type in the Safety Analysis Set. Additionally, the number and percentage of subjects at each visit who tested non-negative for non-opioid substances will be summarized by subject type in the Safety Analysis Set in a tables and in figures for amphetamine, barbiturates, benzodiazepine, cannabinoids, and phencyclidine.

Opioid TLFB and UDS results will be listed together. Additionally, all drugs identified in the TLFB interviews and detected in the UDS will be listed separately for the Safety Analysis Set.

